8.7 Multiplicity

There is only one testable research hypothesis in this study. Formal statistical testing with associated p-value cut-offs centered around controlling Type-I error rates will not be used in assessing this hypothesis; hence no multiplicity adjustment is required or proposed.

8.8 Sample Size and Power Calculations

Pharmacodynamics

This is the first study of MK-5160 in a diabetic patient population, and as such no variance estimates exist other than those from a single dose study in normal healthy volunteers (P001). In order to provide an approximate estimate of power, the variability observed in P001 has been used for the power calculations presented below (Table 9).

Table 9 Probability of Supporting Primary PD Hypothesis

Target GIRmax (mg/kg/min)	True GIRmax	Probability of Supporting Hypothesis
(1.5, 4.5)	1	2%
	1.5	30%
	2	86%
	2.5	99%
	3	99%
	3.5	99%
	4	86%
	4.5	30%
	5	2%

The calculations above were based [REDACTED]
[REDACTED] and N=6 per dose, and a posterior probability threshold of 70%.

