8.0 STATISTICAL ANALYSIS PLAN

8.1 Statistical Analysis Plan Summary

This section contains a brief summary of the statistical analyses for this trial. Full details can be found beginning in Section 8.2).

Statistical Methods

Safety:

Incidence of adverse experiences will be descriptively summarized. Summary statistics and plots will be generated for the change from baseline values in the vital signs, ECG parameters, and selected laboratory safety parameters for subjects, as deemed clinically appropriate. Depending on the safety parameter, the difference from baseline will either be computed on the original scale (raw change from baseline) or on the log scale and back-transformed for reporting (percent change from baseline). Summary statistics for the raw laboratory safety tests, ECGs, and/or vital signs may also be computed, as deemed clinically appropriate. Results will be summarized separately by study part.

Pharmacodynamics

Individual maximal GIR values (GIRmax) based on LOESS smoothed data will be analyzed in a linear mixed effects model with fixed effects for treatment (i.e. glargine, MK-5160 Dose Level 1, MK-5160 Dose Level 2, MK-5160 Dose Level 3), day (Day 1, Day 12) and treatment by day interaction, a continuous covariate for BMI, and a random effect for subject. A separate model will be used for each patient population (T1DM, T2DM).

GIRmax means and 95% confidence intervals for each treatment/day will be calculated from the model. To test the primary hypothesis, the posterior probability that the true mean GIRmax level at steady state is within 1.5 and 4.5 mg/kg/min will be calculated for each MK-5160 dose on Day 12 using a non-informative prior. If this posterior probability exceeds 70% for at least one safe and well tolerated dose of MK-5160 for each population, then the primary research hypothesis will be supported.

Between treatment GIRmax comparisons (MK-5160 versus glargine) will be performed for each dose of MK-5160 and on each day, using the model.

Pharmacokinetics

Non-compartmental Analysis (NCA) based geometric means and 95% confidence intervals will be provided for Cmax, AUC0-24hr, Css and CL by treatment, day and population. The geometric mean accumulation ratio (Day 12 PK / Day 1 PK) and 90% CI will be calculated for Cmax and AUC0-24hr.

Scatterplots of individual PK values (Steady state AUC0-24hr, Cmax, Css) versus BMI will be plotted for each patient population.

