Individual values will be listed for each PK parameter by treatment and day and the additional following (NCA-based) descriptive statistics will be provided: N (number of subjects with non-missing data), arithmetic mean, standard deviation, arithmetic percent CV (calculated as 100 x standard deviation/ arithmetic mean), median, minimum, maximum, geometric mean, and geometric percent CV (calculated as 100 x sqrt(exp(s2) - 1), where s2 is the observed variance on the natural log-scale). For Tmax, only median, minimum and maximum will be calculated.

Pharmacokinetic endpoints following administration with glargine may be summarized in a similar fashion, as appropriate.

Power

Pharmacodynamics

This is the first study of MK-5160 in a diabetic patient population, and as such no variance estimates exist other than those from a single dose study in normal healthy volunteers (P001). In order to provide an approximate estimate of power, the variability observed in P001 has been used for the power calculations presented below (Table 8). [REDACTED]

Table 8 Probability of Supporting Primary PD Hypothesis

Target GIRmax (mg/kg/min)	True GIRmax	Probability of Supporting Hypothesis
(1.5, 4.5)	1	2%
	1.5	30%
	2	86%
	2.5	99%
	3	99%
	3.5	99%
	4	86%
	4.5	30%
	5	2%

The calculations above were based on [REDACTED] and N=6 per dose, and a posterior probability threshold of 70%.

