8.3 Hypotheses/Estimation

Primary:

At a dose with sufficient safety, the mean steady-state maximum level of GIR (GIRmax) after MK-5160 administration in both T1 and T2 DM patients is between 1.5 and 4.5 mg/kg/min.

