8.6 Statistical Methods

Primary

Safety:

Incidence of adverse experiences will be descriptively summarized. Summary statistics and plots will be generated for the change from baseline values in the vital signs, ECG parameters, and selected laboratory safety parameters for subjects, as deemed clinically appropriate. Depending on the safety parameter, the difference from baseline will either be computed on the original scale (raw change from baseline) or on the log scale and back-transformed for reporting (percent change from baseline). Summary statistics for the raw laboratory safety tests, ECGs, and/or vital signs may also be computed, as deemed clinically appropriate. Results will be summarized separately by study part.

The incidence and nature of nighttime and other episodes of potential hypoglycemia, using fingerstick glucose levels and CGM data will be summarized using descriptive statistics. Modeling techniques may be employed as needed.

Pharmacodynamics

Individual maximal GIR values (GIRmax) based on LOESS smoothed data will be analyzed in a linear mixed effects model with fixed effects for treatment (i.e. glargine, MK-5160 Dose Level 1, MK-5160 Dose Level 2, MK-5160 Dose Level 3), day (Day 1, Day 12) and treatment by day interaction, a continuous covariate for BMI, and a random effect for subject. A separate model will be used for each patient population (T1DM, T2DM).

GIRmax means and 95% confidence intervals for each treatment/day will be calculated from the model. To test the primary hypothesis, the posterior probability that the true mean GIRmax level at steady state is within 1.5 and 4.5 mg/kg/min will be calculated for each MK-5160 dose on Day 12 using a non-informative prior. If this posterior probability exceeds

70% for at least one safe and well tolerated dose of MK-5160 for each population, then the primary research hypothesis will be supported.

Between treatment GIRmax comparisons (MK-5160 versus glargine) will be performed for each dose of MK-5160 and on each day, using the model.

Additional clamp endpoints that may be analyzed in a similar fashion as above include GIR AUC endpoints over the entire clamp timeframe (0-24 hours) as well as various subfractions of interest (e.g. 0-12, 12-24 hours), though these would be based on raw data and not LOESS smoothed.

Secondary

Pharmacokinetics

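### Tables 8 and 9 give the chance that one dose passes in one population, not the probability of supporting the primary hypothesis under the plan's own rule

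*Combined protocol and SAP*

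**What the plan says.** Section 8.3 states one primary hypothesis: at a sufficiently safe dose, mean steady-state GIRmax "after MK-5160 administration in both T1 and T2 DM patients is between 1.5 and 4.5 mg/kg/min". Section 8.6 fits a separate mixed model in each population and computes, for each MK-5160 dose on Day 12, the posterior probability that the mean lies in that range under a non-informative prior. The criterion is a probability above "70% for at least one safe and well tolerated dose of MK-5160 for each population, then the primary research hypothesis will be supported". Section 8.1 states the same rule.

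Section 2.1 plans three panels in each of the two parts, with different subjects in each panel. Table 1 assigns six subjects per panel to MK-5160.

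The power statement in section 8.8 is headed "Table 9 Probability of Supporting Primary PD Hypothesis". The same values appear in section 8.1 as "Table 8 Probability of Supporting Primary PD Hypothesis". In both, the last column is named to the same effect. Each row is indexed by one true GIRmax: 2% at 1.0, 30% at 1.5, 86% at 2.0, 99% from 2.5 to 3.5, then 86%, 30% and 2% at 4.0, 4.5 and 5.0. The readable part of the footnote gives "N=6 per dose, and a posterior probability threshold of 70" per cent. The SD and part of the description of the calculation are redacted.

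**The concern.** The rule depends on up to six dose means, three in each population, combined as at least one in T1DM and at least one in T2DM. A table indexed by a single mean, with N=6, cannot express that without further assumptions, and no readable text states any. If the entries are per dose and per population, the heading and the last column misname them.

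These tables are the only power statement in the plan. Requiring both populations lowers the probability, while allowing any of several doses raises it. A reader cannot recover the rule's probability from the tables, or tell whether it lies above or below the printed figure.

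The discrepancy is largest near the limits of the range, and the plan expects to work near the lower one. Section 4.2.3.3 anticipates steady-state GIRmax of 1.0 to 2.0 mg/kg/min, and section 4.2.1 gives a target of 1.5 to 2.0. Section 4.2.2.3 expects roughly 1.5- to 2-fold insulin resistance in T2DM. Section 7.1.5.5 also allows whole panels to be dropped, which leaves fewer doses to satisfy the rule.

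**Working it through.** **Inputs.** Range 1.5 to 4.5 (8.3); threshold 70%, flat prior, separate models (8.6); N=6 per dose (8.8); up to three doses per population (2.1). The SD is redacted, so it is inferred below.

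**Step 1: reproduce the tables as one dose in one population.** With a flat prior, the posterior of the mean is normal around the sample mean with SE = SD/√6. When SE is small relative to the range, a dose passes if its sample mean lies between 1.5 + 0.524·SE and 4.5 − 0.524·SE, where 0.524 is the 70th percentile of the standard normal. Near the lower limit:

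p(μ) = Φ[(μ − 1.5)/SE − 0.524]

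Setting p(2.0) = 0.86 gives 0.5/SE = 1.080 + 0.524 = 1.604. Hence SE = 0.312 and SD = 0.763. Rounding of 86% (85.5 to 86.5%) allows an SD of 0.75 to 0.77.

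| True mean | 1.0 | 1.5 | 2.0 | 2.5 | 3.0 | 3.5 | 4.0 | 4.5 | 5.0 |
|---|---|---|---|---|---|---|---|---|---|
| Tables 8 and 9 | 2% | 30% | 86% | 99% | 99% | 99% | 86% | 30% | 2% |
| One dose, one population | 1.7% | 30.0% | 86.0% | 99.6% | 100.0% | 99.6% | 86.0% | 30.0% | 1.7% |

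All rows agree within 1 point. The 86% rows agree by construction. The 30% at the edges is 1 − 0.70 and hardly depends on the SD: it is still 29.8% at SD 2.0 and falls to 28% only at SD 2.5. Posteriors based on t with 5, 15 or 20 degrees of freedom fit equally well, with SD 0.75 to 0.76.

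**Step 2: can a joint rule produce the same tables?** Take the same true mean in every dose and population, and search SDs from 0.2 to 2.0. The smallest achievable worst-row miss is 21 points for one dose in two populations, 35 for three doses in one, 13 for three doses in two, and 4 for two doses in two (26% against 30% at the edges, although three panels are planned). None matches as the single-dose reading does.

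**Step 3: apply the rule in 8.6.** The populations are independent (different subjects, separate models). Doses are treated as independent and all as safe:

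P(support) = [1 − ∏(1 − p) over T1DM doses] × [1 − ∏(1 − p) over T2DM doses]

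Table values are p(1.0) = 0.02, p(1.5) = 0.30, p(2.0) = 0.86, p(2.5) = 0.99. The dose means are illustrative, since no readable passage gives a dose-response.

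Power, with at least one dose truly in range in each population (86% stated at 2.0):

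| T1DM means | T2DM means | Calculation | Result |
|---|---|---|---|
| 2.0 only | 2.0 only | 0.86² | 74% |
| 1.0/1.5/2.0 | 1.0/1.5/2.0 | (1 − 0.98×0.70×0.14)² = 0.904² | 82% |
| 1.5/2.0 (one panel omitted) | 1.5/2.0 | (1 − 0.70×0.14)² = 0.902² | 81% |
| 1.5/2.0/2.5 | 1.0/1.5/2.0 | 0.999×0.904 | 90% |
| 2.0/2.0/2.0 | 2.0 only | 0.997×0.86 | 86% |
| 2.0/2.0/2.0 | 2.0/2.0/2.0 | (1 − 0.14³)² = 0.9973² | 99.5% |

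False support, with no dose inside the range in at least one population (30% stated at 1.5):

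| T1DM means | T2DM means | Calculation | Result |
|---|---|---|---|
| 1.5 only | 1.5 only | 0.30² | 9% |
| 1.5/1.5/1.5 | 1.5/1.5/1.5 | (1 − 0.70³)² = 0.657² | 43% |
| 1.0/1.5/2.0 | 1.0/1.5 (top panel omitted) | 0.904×(1 − 0.98×0.70) = 0.904×0.314 | 28% |

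At 1.75, the middle of the 4.2.1 target and not tabulated, p = 0.6095 at the inferred SE. The rule gives 0.6095² = 37% with one dose per population and (1 − 0.3905³)² = 88% with three. At 2.5, one dose per population gives 0.99² = 98%.

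**Step 4: check independence between doses.** In 200,000 simulated trials (SD 0.764, one residual variance estimated per population and shared by its doses, t posterior, no BMI term), the 74, 82, 99.5, 90, 28, 9 and 43% cases came out at 73, 82, 99.4, 90, 28, 9 and 43%.

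**The case against.** The strongest case against is that no entry is miscalculated. The single true mean per row and the per-dose N point a statistical reader to the per-dose meaning, so this is a loose heading. The redactions fall where an author would state variance and scope, so hidden text may say the figures are per dose and per population. The effect has no fixed direction, and four of the six power cases above lie within 5 points of 86%. If the mean is taken as proportional to dose and halved in T2DM (T1DM 1/2/4, T2DM 0.5/1/2), the rule gives about 85%. The 74% case needs exactly one viable dose in each population, which no passage predicts. This is Phase 1, no Type I error control is claimed (8.7), and the healthy-volunteer variance may be the larger uncertainty.

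Much of this stands. The entries are correct for what they measure, the scenarios are illustrative, and the plan cannot be said never to define the scope. It does not remove the mismatch. Redacted inputs cannot change the printed title and column heading, which name a different quantity. The per-dose N gives the sample size behind a row and does not say that the result concerns one dose in one population. The plan's caveat, "In order to provide an approximate estimate of power, the variability observed in P001 has been used for the power calculations presented below", concerns the borrowed variance and not a simplified rule. The tables do equal the rule's probability when the other population is almost certain to pass and only one dose is viable in this one, but no readable text states that condition.

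**Conclusion.** The concern holds and should be fixed. The printed figures are single-dose, single-population probabilities labelled as the probability of supporting a hypothesis that needs a passing dose in both populations. In the scenarios shown, the rule's power ranges from 74% to 99.5% against a stated 86%, and its false support from 9% to 43% against a stated 30%. The tables are thus neither uniformly too high nor too low. From 2.5 to 3.5 the difference does not matter.

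That the tables match the single-dose reading is well supported. The size of the gap rests on the inferred SD where the mean is not tabulated, on the illustrative dose means, on approximate independence between doses, and on every dose being judged safe. The safety condition can only lower the figures.

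**What to change.** 1. Retitle Tables 8 and 9 and rename their last column, for example: probability that a single MK-5160 dose (N=6) meets the 70% criterion in one population. This alone removes the mislabelling.
2. So that the plan also states the power of its own rule, add the probability of supporting the hypothesis under 8.6, using the P001 SD the sponsor already holds, for a few T1DM/T2DM dose-response scenarios. Include the anticipated 1.0 to 2.0 range, a lower T2DM response and an omitted panel. Print the assumed means beside each figure and mark which scenarios are power and which are false support.

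The cost is SAP wording and a short calculation. Sample size, decision rule, analysis, conduct and section 8.7 do not change. Some stated figures become less favourable (86% becomes 74% with one viable dose per population at 2.0) and others more favourable.

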9.0 LABELING, PACKAGING, STORAGE AND RETURN OF CLINICAL SUPPLIES

9.1 Investigational Product

The investigator shall take responsibility for and shall take all steps to maintain appropriate records and ensure appropriate supply, storage, handling, distribution and usage of investigational product in accordance with the protocol and any applicable laws and regulations.

Clinical Supplies will be provided by the Sponsor as summarized in Table 10

Clinical supplies will be packaged to support enrollment and replacement subjects as required. When a replacement subject is required, the Sponsor or designee needs to be contacted prior to dosing the replacement supplies.

Table 10 Product Descriptions

Product Name & Potency	Dosage Form	Source/Additional Information
MK-5160, 20.0 mg/mL	Sterile Solution for IV Administration, 1.0 mL per vial	Supplied by Sponsor

All supplies indicated in [Table 10](#) will be provided per the “Source/Additional Information” column depending on local country operational requirements.

Any commercially available product not included in [Table 10](#) will be provided by the trial site, subsidiary or designee. Every attempt should be made to source these supplies from a single lot/batch number. The trial site is responsible for recording the lot number, manufacturer, and expiry date for any locally purchased product as per local guidelines unless otherwise instructed by the Sponsor.

9.2 Packaging and Labeling Information

Clinical supplies will be affixed with a clinical label in accordance with regulatory requirements.

Subjects will receive open label vials. No kitting is required.

9.3 Clinical Supplies Disclosure

The emergency unblinding call center will use the randomization schedule for the trial to unblind subjects and to unmask treatment identity. The Sponsor will not provide random code/disclosure envelopes or lists with the clinical supplies.

9.4 Storage and Handling Requirements

Clinical supplies must be stored in a secure, limited-access location under the storage conditions specified on the label.

Receipt and dispensing of trial medication must be recorded by an authorized person at the trial site.

Clinical supplies may not be used for any purpose other than that stated in the protocol.

9.5 Discard/Destruction>Returns and Reconciliation

The investigator is responsible for keeping accurate records of the clinical supplies received from the Sponsor or designee, the amount dispensed to and returned by the subjects and the amount remaining at the conclusion of the trial. For all trial sites, the local country Sponsor personnel or designee will provide appropriate documentation that must be completed for drug accountability and return, or local discard and destruction if appropriate. Where local discard and destruction is appropriate, the investigator is responsible for ensuring that a local discard/destruction procedure is documented.

10.0 ADMINISTRATIVE AND REGULATORY DETAILS

10.1 Confidentiality

10.1.1 Confidentiality of Data

By signing this protocol, the investigator affirms to the Sponsor that information furnished to the investigator by the Sponsor will be maintained in confidence, and such information will be divulged to the institutional review board, ethics review committee (IRB/ERC) or similar or expert committee; affiliated institution and employees, only under an appropriate understanding of confidentiality with such board or committee, affiliated institution and employees. Data generated by this trial will be considered confidential by the investigator, except to the extent that it is included in a publication as provided in the Publications section of this protocol.

10.1.2 Confidentiality of Subject Records

By signing this protocol, the investigator agrees that the Sponsor (or Sponsor representative), IRB/ERC, or regulatory authority representatives may consult and/or copy trial documents in order to verify worksheet/case report form data. By signing the consent form, the subject agrees to this process. If trial documents will be photocopied during the process of verifying worksheet/case report form information, the subject will be identified by unique code only; full names/initials will be masked prior to transmission to the Sponsor.

By signing this protocol, the investigator agrees to treat all subject data used and disclosed in connection with this trial in accordance with all applicable privacy laws, rules and regulations.

10.1.3 Confidentiality of Investigator Information

By signing this protocol, the investigator recognizes that certain personal identifying information with respect to the investigator, and all subinvestigators and trial site personnel, may be used and disclosed for trial management purposes, as part of a regulatory submissions, and as required by law. This information may include:

1. name, address, telephone number and e-mail address;
2. hospital or clinic address and telephone number;
3. curriculum vitae or other summary of qualifications and credentials; and
4. other professional documentation.

Consistent with the purposes described above, this information may be transmitted to the Sponsor, and subsidiaries, affiliates and agents of the Sponsor, in your country and other countries, including countries that do not have laws protecting such information. Additionally, the investigator's name and business contact information may be included when reporting certain serious adverse events to regulatory authorities or to other investigators. By signing this protocol, the investigator expressly consents to these uses and disclosures.

If this is a multicenter trial, in order to facilitate contact between investigators, the Sponsor may share an investigator's name and contact information with other participating investigators upon request.

10.1.4 Confidentiality of IRB/IEC Information

The Sponsor is required to record the name and address of each IRB/IEC that reviews and approves this trial. The Sponsor is also required to document that each IRB/IEC meets regulatory and ICH GCP requirements by requesting and maintaining records of the names and qualifications of the IRB/IEC members and to make these records available for regulatory agency review upon request by those agencies.

10.2 Compliance with Financial Disclosure Requirements

Financial Disclosure requirements are outlined in the US Food and Drug Administration Regulations, Financial Disclosure by Clinical Investigators (21 CFR Part 54). It is the Sponsor's responsibility to determine, based on these regulations, whether a request for Financial Disclosure information is required. It is the investigator's/subinvestigator's responsibility to comply with any such request.

The investigator/subinvestigator(s) agree, if requested by the Sponsor in accordance with 21 CFR Part 54, to provide his/her financial interests in and/or arrangements with the Sponsor to allow for the submission of complete and accurate certification and disclosure statements. The investigator/subinvestigator(s) further agree to provide this information on a Certification/Disclosure Form, commonly known as a financial disclosure form, provided by the Sponsor. The investigator/subinvestigator(s) also consent to the transmission of this information to the Sponsor in the United States for these purposes. This may involve the transmission of information to countries that do not have laws protecting personal data.

